# Preparation for Dose Level -1

# **PVSRIPO Dilution for Dose Level -1:**

- To measure to PVSRIPO dose, we must make a 1:10 dilution.
- Dilute 0.5 ml (1 vial) PVSRIPO with 4.5 ml of Vehicle (phosphate-buffered saline, 0.2% human serum albumin) in a syringe. Refer to table 2 for remainder of steps needed for preparation.

Dose level	PVSRIPO dose (In 3 mL)	PVSRIPO (in 8 mL total syringe load)	Diluted 1:10 (see above) PVSRIPO	Previously Diluted (1:10) gadopentetate dimeglumine (Magnevist®)	Vehicle (phosphate- buffered saline, 0.2% human serum albumin)	Total Volume in 20 ml syringe
-1	5 x 10  TCID50	1.33 x 10  TCID50	0.33 mL	0.16 mL	7.51 mL	8 mL

#### Preparation for Dose Level -2 PVSRIPO Dilution for Dose Level -2:

- To measure to PVSRIPO dose, we must make a 1:100 dilution.
- Dilute 0.5 ml (1 vial) PVSRIPO with 49.5 ml of Vehicle (phosphate-buffered saline, 0.2% human serum albumin) in a syringe. Refer to table 3 for remainder of steps needed for preparation.

Dose level	PVSRIPO dose (In 3 mL)	PVSRIPO (in 8 mL total syringe load)	Diluted 1:100 (see above) PVSRIPO	Previously Diluted (1:10) gadopentetate dimeglumine (Magnevist®)	Vehicle (phosphate- buffered saline, 0.2% human serum albumin)	Total Volume in 20 ml syringe
-2	1 x 10  TCID50	2.67 x 10  TCID50	0.67 mL	0.16 mL	7.17 mL	8 mL

Administration. The study agent will be administered to patients via intracerebral delivery using a previously implanted tube radiographically determined to be placed correctly within the tumor bed. The syringe containing the study agent (upon delivery from the Investigational Pharmacy) will be connected to the tube equipped with the appropriate adaptor. This occurs by removing the cap and fastening the syringe to the Luer-Lok adaptor and does not involve needles. The infusion procedure is driven by an infusion pump at a set pace measured to last ~6 hrs. The infusion procedure will take place in dedicated space in the Neurosurgical ICU or the Neuro Step-Down Unit, where patients will remain overnight for observation.

The infusion procedure in the Neurosurgical ICU or the Neuro Step-Down Unit follows established principles, e.g. those previously used for delivery of radiochemicals by a similar infusion method and under similar containment precautions. All procedures are restricted to a single room where the patient remains throughout the duration of the infusion. Access to the room is restricted to staff caring for the patient.

For reasons pointed out above, persons involved with the care of patients enrolled in the study and who received the standard recommended poliovirus vaccine schedule as a child, are not required to be re-vaccinated.

All materials coming in contact with the study agent, the syringe delivered from the Investigational Pharmacy, tubing, dressings or coverings used to protect the trepanation site, will be disposed of as biological waste in the treatment room. All personnel caring for the patient will be wearing appropriate safety devices, e.g. disposable gloves, gown, and face protection, which will be disposed of as biological waste in the treatment room. Appropriate hand hygiene is required before and after any handling of the study agent

**Disposal.** All surgical materials used in the procedure and (potentially) coming in contact with the study agent will be disposable. These materials will be disposed of as biological waste using established procedures. Used sharps will be disposed in biohazard sharps container and incinerated for final disposal.

#### List of locations.

- Investigational Pharmacy (receipt, storage, aliquot preparation)
- Closed transport container; at 4°C (for transport of the sealed delivery device containing the study agent)
- Study site in the Neurosurgical ICU or the Neuro Step-Down Unit (administration)

• Investigational Pharmacy (disposal of unused or partially used study agent)

**Spill procedure.** PVSRIPO can all be easily and completely inactivated with household bleach. In the event of a spill, the liquid will be absorbed with gauze (then treated as biohazardous waste as above). The spill area will then be liberally wiped down with a 20% household bleach solution for chemical disinfection. The disinfectant will be left in contact with contaminated area for at least 30 minutes, then wiped away with wet towels, which will be disposed as biohazard waste as well.

**Exposure follow-up.** Any virus exposures will be reported to the Employee Health Exposure Hotline (115), followed by submission of the Report of Occupational Injury or Illness form. There is no specific preventative treatment. Based on the circumstances of exposure, employee health may choose to monitor for infection by submitting stool for enterovirus culture at 7, 14, and 21 days after an exposure event.

## 18.4. SELECTION AND DESCRIPTION OF THE HISTORICAL CONTROL COHORT

The historical cohort that will be used for the evaluation of PVSRIPO efficacy among WHO grade IV malignant glioma patients was derived from the PRoGREss registry (IRB# Pro00027120; Primary and Recurrent Glioma Registry).

Description of PRoGREss registry: The PRoGREss registry study is both a retrospective and prospective chart review study of all patients diagnosed after 12/31/2004 with a primary CNS tumor who were seen at the PRTBTC. Specifically, that database includes: (1) data from all patients that were deceased as of 11/3/2011, and (2) data collected retrospectively and prospectively from patients who were alive as of 11/3/2011 and provided registry consent. The latter group includes patients who were diagnosed after 12/31/2004 but before 11/3/2011, as well as patients diagnosed after 11/3/2011. Both demographic and clinical information was extracted from clinical and research records, which included such information as diagnosis, gender/race/ethnicity, medical history, medications, and types of treatment. Details about the data available from the PRoGREss registry can be found in the PRoGREss protocol.

Criteria Used to Select Historical Control Cohort: To create the historical cohort, data available from the PRoGREss registry as of 12/15/2014 were reviewed to determine which patients would have been eligible to participate in the PVSRIPO phase I study at the time their disease recurred in 2007 or later. All radiologic records were reviewed by [name] without knowledge of the patient's survival outcome in making this determination.

During the conduct of the PVSRIPO WHO grade IV malignant glioma Phase I study, most modifications to the patient eligibility criteria were minor. As such, the eligibility criteria used for identifying the historical control cohort from the PRoGREss registry were standardized. The following relevant criteria were used:

- 1. Patients must have a diagnosis of recurrent supratentorial WHO Grade IV MG based on imaging studies with measurable disease (≥ 1 cm and ≤ 5.5 cm of contrast-enhancing tumor)
- 2. Age  $\geq$  18 years of age
- 3. Patients must not have taken part in the PVSRIPO study
- 4. KPS ≥70 at the time patient could have been enrolled on the PVSRIPO study
- 5. Absence of rapid clinical decline

After the first 5 patients were treated at dose level "-1," the PVSRIPO WHO grade IV malignant glioma Phase I study was amended to institute a limit on pre-treatment steroid usage to  $\leq$  4 mg per day of dexamethasone within the 2 weeks prior to admission for PVSRIPO infusion. There were no steroid limitations for all patients treated on dose levels 1-5 and for the first 5 patients treated on dose level "-1". To address this eligibility amendment, two control groups have been generated, with one group having no limitations on pre-treatment steroid usage, and the other group having a steroid limit of  $\leq$  4 mg per day of dexamethasone (or equivalent) within the 2 weeks prior to being eligible for PVSRIPO infusion.

Within these historical control cohorts, survival time was computed as the time between the date of the first MRI at which time the patient would have been eligible to receive PVSRIPO and the date of death. If the patient remained alive at the date of last follow-up, survival time was censored at that date.

Characteristics of the Patients within the Historical Control Group: A summary of selected patient characteristics in these two historical control groups is provided below.

		Gro	oup		
Patient Characteristics	con with s	orical trols steroid led pts)	Historical controls (without steroid expanded pts)		
	Ν	%	Ν	%	
All	124	100.0	104	100.0	
Gender					
Female	44	35.5	39	37.5	
Male	80	64.5	65	62.5	
Histologic Diagnosis					
GBM	124	100.0	104	100.0	
Age at GBM Diagnosis, mean (SD)	55.3	(10.9)	54.7	(11.2)	
Age at GBM Diagnosis, median (range)	55 (20	) – 76)	54 (20	0 – 76)	
Primary or Secondary GBM					
Primary	110	88.7	92	88.5	
Secondary	13	10.5	11	10.6	
Unknown	1	0.8	1	1.0	
Karnofsky Performance Status					
100	8	6.5	8	7.7	
90	69	55.6	64	61.5	
85	2	1.6	2	1.9	
80	36	29.0	27	26.0	
70	7	5.6	2	1.9	
Undetermined but ≥70	2	1.6	1	1.0	
Resection Type at diagnosis*					
GTR	73	58.9	60	57.7	
STR	29	23.4	25	24.0	
Biopsy	22	17.7	19	18.3	
Further Surgery prior to Treatment**					
GTR	8	6.5	8	7.7	
STR	6	4.8	4	3.8	
None	110	88.7	92	88.5	
PDs prior to being eligible	102	82.3	85	81.7	

	Group						
Patient Characteristics	con with s(	orical trols steroid led pts)	Historical controls (without steroid expanded pts				
	Ν	%	Ν	%			
1							
2	14	11.3	12	11.5			
3	8	6.5	7	6.7			
Total Daily Dex (or other steroid) dose at MRI							
0	89	71.8	89	85.6			
0.125	1	0.8	1	1.0			
0.5	1	0.8	1	1.0			
1	1	0.8	1	1.0			
2	3	2.4	3	2.9			
4	8	6.5	8	7.7			
6	2	1.6	0	0			
8	4	3.2	0	0			
12	4	3.2	0	0			
14	1	0.8	0	0			
16	3	2.4	0	0			
30 mg Hydrocortisone	1	0.8	1	1.0			
Unknown	6	4.8	0	0			
Avastin prior to eligible PD							
No	61	49.2	49	47.1			
Yes	63	50.8	55	52.9			
Avastin Failure prior to eligible PD							
No	75	60.5	61	58.7			
Yes	49	39.5	43	41.3			
Vital Status							
Alive	1	0.8	1	1.0			
Dead	123	99.2	103	99.0			

\*In both control groups, this includes 1 patient with a questionable STR/GTR, and 1 patient with a GTR on the primary tumor and a STR on a second tumor. \*\*In both control groups, this includes 1 patient with a questionable STR/GTR.

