#### 9.2.5. Prior Therapy

Patients who have not recovered from the toxic effects of prior chemotherapy and/or radiation therapy will be excluded. Guidelines for this recovery period are dependent upon the specific therapeutic agent being used.

• Patients may not have received chemotherapy or bevacizumab ≤ 4 weeks [except for nitrosourea (6 weeks) or metronomic dosed chemotherapy such as daily

etoposide or cyclophosphamide (1 week)] prior to starting the study drug unless patients have recovered from side effects of such therapy.

- Patients may not have received immunotherapy ≤ 4 weeks prior to starting the study drug unless patients have recovered from side effects of such therapy.
- Patients may not be less than 12 weeks from radiation therapy, unless progressive disease outside of the radiation field or 2 progressive scans at least 4 weeks apart or histopathologic confirmation.
- Patients must have completed all standard of care treatments, including surgical procedure and radiation therapy (at least 59Gy)
  - If the MGMT promoter in their tumor is known to be unmethylated, patients are not mandated to have received chemotherapy prior to participating in this trial.
  - If the MGMT promoter in their tumor is known to be methylated or the MGMT promoter status is unknown at the time of screening, patients must have received at least one chemotherapy regimen prior to participating in this trial.

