#### 9.2.6. Location and Extent of Tumor

Because of the potential toxicities from the agent, patients with neoplastic lesions in the brainstem, cerebellum or spinal cord, radiological evidence of active (growing) multifocal disease, or leptomeningeal disease will be excluded. Patients with evidence of diffuse subependymal disease or tumor in the brainstem, cerebellum, spinal cord, or CSF will also be excluded.

Since the study agent is a local treatment, patients with radiological evidence of active (growing) multifocal disease, tumors extending into or crossing the corpus callosum or leptomeningeal disease, will be excluded.

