#### 14.3.1. Dose Expansion at Dose Level "-1"

Accrual at dose level -1 will be extended in order that a sufficient number of patients will be treated at that dose level to estimate its efficacy relative to a historical cohort.

As of 6/15/2015, 28 patients have been treated on this protocol, including 13 patients treated at dose level -1. The median survival is 15.2 months (95% confidence interval: 7,  $\infty$ ). Median follow-up among patients treated at dose level -1 is 3.5 months.

Informal comparisons of survival associated with PVSRIPO (including all patients at all dose levels) relative to that observed in other recurrent WHO grade IV malignant glioma patient groups suggest a hazard ratio in the ballpark of 0.5 to 0.65.

The historical cohort that will be used for this comparison will include recurrent WHO grade IV malignant glioma patients in the PRoGREss registry (IRB# Pro00027120; Primary and Recurrent Glioma Registry) who would have been eligible to receive PVSRIPO if the treatment had been available. Details about the construction of this comparison group, as well as a summary of control group patient characteristics are provided in Appendix 18.4. Two control groups were generated, with one group having no limit to pre-treatment steroid usage, and the other group having a steroid limit of  $\leq$  4 mg per day of dexamethasone within the 2 weeks prior to being eligible for PVSRIPO infusion. The first control group has eligibility criteria similar to that which was in existence for dose levels 1-5 and the first 5 patients on dose level "-1". The second control group has eligibility criteria similar to those currently being used for dose level "-1". The first historical control group includes 124 patients of which 123 are dead; whereas, the second historical control group includes 104 patients of which 103 are dead.

Korn and Friedlin (48) recommend the use of an unconditional power estimator for the determination of sample size in single arm studies that compare time-to-event outcomes such as survival with that observed in a historical control group. That estimator resembles an estimator for a 2-arm randomized study. The power of such a comparison is dependent upon the total number of observed deaths (49).

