The ultimate goal of this accrual expansion and survival comparison is to determine whether PVSRIPO administered at dose level -1 and, as needed, with a radiation-necrosis dose level and schedule of bevacizumab in the manner described within this protocol has merit for further evaluation in additional clinical studies. This goal is analogous to that of a randomized phase II screening study, except for the fact that the two groups are not created by randomization. The second historical control group will be considered in this comparison. Typically, with a randomized phase II study, there is a need to constrain the sample size requirements at the expense of either an increased false negative or false positive rate. It has been recommended that a false-positive rate of 0.2 be used to test a hypothesis comparing arms while maintaining a high power level (e.g. 90%).

A total of 50 subjects will be accrued and treated at dose level -1. Assuming survival is exponentially distributed and the median survival associated with the -1 dose level is 15.2 months, we anticipate that approximately 15 of the 50 patients will be deceased by the time accrual is complete in June 2016. Without additional follow-up, the power of a logrank test conducted at the 0.2 level of significance (one-tailed) to detect a hazard ratio of 0.5, 0.55, 0.6, and 0.65 are 0.95, 0.91, 0.84, and 0.76, respectively. Tabulated below is the power to detect these hazard ratios as a function of the number of additional months of follow-up after accrual completion (Table 4).

Follow-	Expected # Dead if Median OS = 15.2 months	Power of Comparison to Detect Noted Hazard Ratio						
up (Months)		Hazard Ratio = 0.5	Hazard Ratio = 0.55	Hazard Ratio = 0.6	Hazard Ratio = 0.65			
0	15	0.95	0.91	0.84	0.76			
1	16	0.96	0.92	0.85	0.78			
2	18	0.97	0.93	0.88	0.80			
3	19	0.97	0.94	0.89	0.81			
4	21	0.98	0.95	0.90	0.83			
5	22	0.98	0.96	0.91	0.84			
6	23	0.98	0.96	0.91	0.85			
7	24	0.99	0.96	0.92	0.85			
8	26	0.99	0.97	0.93	0.87			
9	27	0.99	0.9	0.94	0.87			
10	28	0.99	0.97	0.94	0.88			
11	29	0.99	0.98	0.94	0.89			
12	30	0.99	0.98	0.95	0.89			

Table 4. Power of the survival comparison to detect the noted hazard ratios

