Given that the study is not a randomized study, there is a need to statistically adjust survival comparisons for confounding factors. Hence, survival comparisons will be conducted using the Cox model. Predictors within the Cox model will include treatment, age, extent of resection, prior bevacizumab treatment, Karnofsky performance status at the time of PVSRIPO treatment, number of prior recurrences, and an indicator of secondary GBM.

It should be noted that the calculations and analyses described above assume that survival with PVSRIPO is exponentially distribution and that the proportional hazards assumption is satisfied. Recently reported studies suggest that such properties may not exist for immunotherapeutic agents due to (1) delayed antitumor effects and hence delayed separation of survival curves, and (2) a percentage of patients who are "cured" or survive for a relatively long period of time. If that is the situation with PVSRIPO, the power calculations and planned analyses may not be appropriate. It might be more appropriate to focus on long-term survivorship at a specific time point such as 18 and 24-month survival. Within the second historical control group, the 18 and 24-month survival probabilities are 23.1% and 13.5%, respectively. A two-tailed chi-square test ( $\alpha$ =0.2) conducted to compare the proportion of patients alive at 18 or 24 months at the 0.2 level has >84% power to detect an increase of 15% in survivorship. Logistic regression will be used to adjust for confounding factors.

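### The level -1 comparison uses steroid-limited controls for all treated patients although the first 5 had no steroid limit, and section 18.4 does not show that the tumour-extent and prior-therapy exclusions were applied to controls

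*Combined protocol and SAP*

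**What the plan says.** Section 14.3.1 defines the historical cohort as registry patients "who would have been eligible to receive PVSRIPO if the treatment had been available". Section 18.4 turns this into a rule: "the eligibility criteria used for identifying the historical control cohort from the PRoGREss registry were standardized. The following relevant criteria were used". Five criteria follow: recurrent supratentorial grade IV tumour with 1 to 5.5 cm of enhancement; age 18 or over; not in the PVSRIPO study; KPS 70 or more; no rapid clinical decline. The second control group (104 patients, 103 dead) also requires dexamethasone of at most 4 mg/day in the preceding 2 weeks. The first group (124 patients, 123 dead) has no such limit.

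For treated patients, section 9.2.6 also excludes active multifocal and diffuse subependymal disease, and states that "tumors extending into or crossing the corpus callosum or leptomeningeal disease, will be excluded". Section 9.2.5 states "Patients may not be less than 12 weeks from radiation therapy", with three exceptions, and sets rules on washout, radiation dose and prior chemotherapy.

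On steroids, section 18.4 says "There were no steroid limitations for all patients treated on dose levels 1-5 and for the first 5 patients treated on dose level" -1. Section 14.3.1 says the first control group resembles the eligibility of levels 1-5 and of those 5 patients, but names the second group for the level -1 comparison. On adjustment it says: "Predictors within the Cox model will include treatment, age, extent of resection, prior bevacizumab treatment", then KPS, number of prior recurrences and secondary GBM.

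**The concern.** Nothing is randomized, so the efficacy reading depends on controls and treated patients having been chosen by the same rules. There are two gaps.

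- **Selection list.** It restates size, age and KPS, and adds a criterion that section 9 does not contain (no rapid decline). It is silent on most of 9.2.6 and on all of 9.2.5. If controls with more extensive disease were kept, control survival would be lower than among eligible patients, in PVSRIPO's favour. The level -2 comparison uses the same 104 controls.
- **Steroid rule.** Two control groups were built because the steroid rule changed, yet level -1, which straddles the change, is compared with only one. If any of the first 5 needed higher doses, and if steroid need is adverse (an assumption), this works against PVSRIPO.

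The false-positive rate is set at 0.2, so a modest shift in the control rate can change whether the drug is judged to merit further study.

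**Working it through.** **1. The plan's own figure.** Inputs from section 14.3.1: 15 expected treated deaths, 103 control deaths, log-rank test at one-sided 0.2. With variance of the log hazard ratio = 1/15 + 1/103 = 0.0764 (SE 0.276), power = Φ(−ln HR / 0.276 − 0.842). For HR 0.5, 0.55, 0.6 and 0.65 this gives 0.952, 0.907, 0.843 and 0.763. The plan states power "to detect a hazard ratio of 0.5, 0.55, 0.6, and 0.65 are 0.95, 0.91, 0.84, and 0.76, respectively". The first row of Table 4 is reproduced. It measures precision and says nothing about bias.

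**2. Listed rules side by side.**

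| Rule for treated patients | Named in the control list? |
|---|---|
| Supratentorial, 1 to 5.5 cm | Yes |
| Age, KPS | Yes |
| Dexamethasone ≤4 mg/day | Second group only |
| Active multifocal disease (9.2.6) | No |
| Into or across corpus callosum (9.2.6; absent from the section 5 synopsis) | No |
| Leptomeningeal, diffuse subependymal (9.2.6) | No |
| 12 weeks from radiotherapy, with exceptions (9.2.5) | No |
| Washout, ≥59 Gy, prior chemotherapy (9.2.5) | No |

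The characteristics table in 18.4 reports none of the items marked No, so the text cannot settle whether they were applied.

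**3. Size of the steroid mismatch.** 5/50 = 10% of the planned level -1 cohort; 5/23 = 22% of those treated at that level by 6/15/2016 (section 11.3.8).

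**4. Cost of leaving out those 5.** Use the plan's exponential survival with a 15.2-month median, and assume 12 to 20 months of follow-up for the 5. Expected deaths lost = 5 × (1 − 2^(−t/15.2)) = 2.1 to 3.0, leaving 12 to 13.

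| Treated deaths | HR 0.5 | 0.55 | 0.6 | 0.65 |
|---|---|---|---|---|
| 15 | 0.952 | 0.907 | 0.843 | 0.763 |
| 13 | 0.935 | 0.883 | 0.814 | 0.733 |
| 12 | 0.924 | 0.868 | 0.798 | 0.716 |

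The loss is about 2 to 5 points.

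**5. Illustration of the selection gap.** Let a fraction f of the 104 controls fail the unlisted exclusions, with h times the hazard of the rest. Both are assumed; the documents give neither. The observed 24-month control rate is 13.5% (section 14.3.1), so the rate s among eligible controls solves (1 − f)s + f·s^h = 0.135.

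| f | h = 1.25 | h = 1.5 | h = 2 |
|---|---|---|---|
| 0 | 13.5% | 13.5% | 13.5% |
| 10% | 14.0% | 14.4% | 14.8% |
| 15% | 14.3% | 14.9% | 15.5% |
| 25% | 14.9% | 15.9% | 17.0% |

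Now give an ineffective drug survival s and compare it with 104 controls at 13.5%, using the unadjusted two-tailed chi-square at 0.2 and counting only rejections in the drug's favour (exact binomial enumeration):

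| s | n = 50 | n = 31 |
|---|---|---|
| 13.5% | 10.8% | 11.0% |
| 14.9% | 15.8% | 15.3% |
| 17.0% | 25.3% | 23.0% |

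The 31 is inferred from dated counts. By 6/15/2015, 28 − 13 = 15 patients had been treated at other levels. By 1/20/2017, 51 − 15 − 23 = 13 more had been treated, taken as level -2. The shedding report has 59 subjects, and 59 − 15 − 13 = 31 if all later patients received level -1.

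These figures redraw the controls at random. Holding them at the observed 14/104 (13.5%) instead, the chance at n = 31 is 4.9% for s = 13.5%, 8.0% for 14.9% and 14.4% for 17.0%.

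**The case against.** A reader might infer that ineligible controls were kept and that the two groups are different populations. The documents do not support that. Section 18.4 says registry data were reviewed for patients who would have been eligible, with radiology read without knowledge of survival. Survival is counted from the first MRI at which the patient would have qualified, and the list is offered as the relevant criteria. Unlisted exclusions may have been applied, so the share of failing controls may be zero, where the bias vanishes. This stands, and limits the first part of the point to missing documentation.

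A reader might also infer that the first 5 level -1 patients were on high steroid doses. Their doses are not given; they were only not subject to a limit.

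Other points stand in part. Site and size are screened. The Cox model covers prior bevacizumab, number of recurrences, KPS, extent of resection and secondary GBM, which meets some of the prior-therapy concern. For level -1 the chi-square test is an alternative, and the plan would adjust it by logistic regression, so the illustration is not the main analysis. Efficacy is a secondary, screening aim, and section 13.3 urges care in reading survival. None of this gives a rule for the first 5 patients or puts tumour extent or steroid dose among the named Cox covariates.

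**Conclusion.** The point holds in two parts of different strength.

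- **Steroid mismatch: explicit.** All level -1 patients are to be compared with the steroid-limited second group, although sections 14.3.1 and 18.4 place the first 5 outside that rule. It affects 10% of the planned cohort, or 22% of those treated by 6/15/2016. It does not touch level -2, which opened after the limit was in force.
- **Unlisted exclusions: a gap in documentation.** The groups are not shown to be the same population, and equally it is not shown that ineligible controls were kept.

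The two may act in opposite directions, so neither the size nor the sign of the net bias can be read from the result. Under the assumed 0 to 25% failing at 1.25 to 2 times the hazard, an ineffective drug's chance of passing the unadjusted 24-month test rises from about 11% to at most about 25% (n = 50) or 23% (n = 31). This illustrates sensitivity and does not estimate the bias. Table 4's first row is arithmetically sound, but no power figure answers this question.

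**What to change.** 1. **First 5 patients.** Make the level -1 comparison with the second control group on patients enrolled under the steroid limit, or pre-specify this as a sensitivity analysis. Also report all level -1 patients against the first, 124-patient group. Cost: about 2 to 3 treated deaths and 2 to 5 points of power where the 5 are left out.
2. **Control screening.** Before the comparison, and blind to survival, check the 104 existing records against section 9.2.6 and the 12-week radiotherapy rule of 9.2.5 with its exceptions. Drop those who fail, state which criteria the registry cannot assess, and restate the 18- and 24-month control rates (now 23.1% and 13.5%). Cost: one re-screen of existing records and possibly somewhat fewer controls.
3. **Corpus callosum.** Reconcile section 9.2.6 with the section 5 synopsis first, so that controls are held to the rule applied to treated patients.

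A dexamethasone covariate should not be relied on instead. No second-group control is listed above 4 mg and 89 of 104 took none, so the model would extrapolate for any treated patient on a higher dose.
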